#### Expected biases to the study

There are several risks for biases as already described in chapter 2.3 *Study design*. With regard to the method, it must be noted that the effect of psychotherapy is multifactorial and thus difficult to control whether any effects are only due to the difference of the specific method (MI) compared to supportive talks (as a control intervention). In order to control for other possible influencing factors, the level of training of the therapists will be included and controlled for. The degree of motivation for psychotherapy of the patients before the beginning of the intervention as well as the attitude towards recovery on the therapist's side can also influence the outcome of a psychotherapeutic intervention, independent of the method. These specific variables will also be included in our calculations. In addition, it is possible that expectation or attitude toward one of the two therapy methods may have an effect on the outcomes. We will therefore blind the study so that patients do not know which group they belong to ("single-blind").

### 3.4 Withdrawal and discontinuation

Participants have the right to abort the study at any point and without providing a reason. The principal investigator and the co-investigator have the right to withdraw participants if they knowingly provide incorrect information, withdraw consent, do not adhere to protocol requirements (i.e. missing appointments, ignoring instructions) or if the disease has progressed (see exclusion criteria).

If participants do not finish the experiment, the data will be stored properly and taken into analysis as far as possible and useful. Additional participants will be recruited to replace the withdrawn participants.

Since they are inpatients, there is a very low risk of missed appointments. If this is still the case, the appointments can be made up on the following day.

If participants are discharged before the end of the study, they may attend the remaining appointments as outpatients if the majority of the study has already taken place (at least 3 psychotherapy sessions must have taken place during inpatient treatment).

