### **2.2 Primary and secondary endpoints**

Primary endpoints are the therapeutic alliance as assessed with the *Scale to Assess Therapeutic Relationship STAR* (McGuire-Snieckus et al., 2007) and adherence to treatment as measured with the *Brief Adherence Rating Scale BARS* (Byerly et al., 2008). These variables will be measured before and after the study intervention or control intervention.

Secondary endpoints include changes in symptom severity as assessed with the *Positive and*

*Negative Symptom Scale PANSS* (Kay et al., 1987), as well as the motivation for psychotherapy (measured with the German version of the *Questionnaire to measure the motivation for psychotherapy* by Schulz et al., 1995) and self-efficacy (measured with the *General Self-Efficacy Scale* by Schwarzer & Jerusalem, 1995). All secondary variables will be measured before and after the study intervention or control intervention.

As this study (risk category A) does not include drugs or other medical products and patients are hardly exposed to any more risks than in routine clinical care, no safety endpoints are defined.

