## 4 STATISTICS AND METHODOLOGY

### 4.1. Statistical analysis plan and sample size calculation

Hypothesis 1: Four sessions of motivational interviewing for newly admitted acute patients (within the first 7 days of hospitalization) improve the therapeutic alliance and the adherence for treatment compared to supportive counseling.

Statistical analysis for hypothesis 1: To apply the statistically most sensitive test, we will use an ANCOVA to analyze the treatment effect of motivational interviewing compared to supportive counseling, with baseline values used as covariates.

Hypothesis 2: Four sessions of motivational interviewing for newly admitted acute patients decreases symptom severity compared to supportive counseling.

Statistical analysis for hypothesis 2: We will use an ANCOVA to analyze the treatment effect of motivational interviewing compared to supportive counseling, with baseline values used as covariates.

Hypothesis 3: Patients show higher motivation to seek psychotherapeutic treatment and have a higher self-efficacy expectation after leaving the inpatient stay, when they received an intervention with motivational interviewing compared to supportive counseling.

Statistical analysis for hypothesis 3: We will use an ANCOVA to analyze the treatment effect of motivational interviewing compared to supportive counseling, with baseline values used as covariates.

Additional calculations: We also want to investigate how the number of hospitalization days and the severity of symptoms at the beginning of the intervention have an influence on the therapy outcome. We calculate this with a multiple regression with days of hospitalization and/or the PANSS total score as independent variables. The treatment outcome is defined as the delta between symptoms before and after the intervention and serves as dependent variable.

General statistical considerations: We will use routine procedures of data processing and use data transformation if necessary (in case of non-normal distribution). Standard statistical calculations will be computed. The level of significance will be set to  $p < 0.05$  (two tailed). Effect sizes will be calculated for significant results. The IBM® SPSS Statistics® statistical software as well as the program R will be used.

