#### 4.2. Handling of missing data and drop-outs

All patients who completed the study will be taken into analysis. All collected data will be checked at each study assessment, and missing data will thus be avoided as much as possible. If missing data nevertheless does occur, data has to be excluded.

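### Investigators may withdraw and replace patients for undefined disease progression, and only completers are analysed, so worsened patients can drop out of the Hypothesis 2 PANSS comparison because of their outcome

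*Combined protocol and SAP*

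**What the plan says.** All references are to the combined protocol and SAP.

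- **Withdrawal (3.4).** "The principal investigator and the co-investigator have the right to withdraw participants" on several grounds, the last being "or if the disease has progressed (see exclusion criteria"). This is a right, not a duty.
- **Replacement (3.4).** "Additional participants will be recruited to replace the withdrawn participants".
- **Non-finishers (3.4).** Their data are to be kept and used where feasible and worthwhile. No rule is given.
- **Analysis set (4.2).** "All patients who completed the study will be taken into analysis", and "If missing data nevertheless does occur, data has to be excluded". The paragraph on the analysis population in 4.1 allows a single population for every hypothesis.
- **Outcome and model.** PANSS is a secondary endpoint and the Hypothesis 2 outcome. Section 2.2 states: "All secondary variables will be measured before and after the study intervention or control intervention". The model, worded alike for all three hypotheses in 4.1, is: "we will use an ANCOVA to analyze the treatment effect of motivational interviewing compared to supportive counseling, with baseline values used as covariates".
- **Schedule (3.3, Table 2).** Randomisation is at visit 1. PANSS and the eligibility check are at visit 2 (day 0). The post-measurement is visit 7 (day 10).
- **Blinding.** Section 2.3 calls the trial open label, then single-blind with blinded raters; 3.3 says patients are blinded. Nothing is said about blinding those who decide on withdrawal, and the principal investigator prepares the block schema.

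**The concern.** Worsening of psychosis is close to what PANSS measures. A rule that lets investigators remove worsened patients, followed by an analysis of those who remain, selects on the outcome. Replacement restores the head count, so reaching 64 per arm would not reveal the loss. Worsening is foreseeable: 5.2 names a flare of psychotic symptoms as something that may happen during the study.

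Two kinds of bias are possible. If worsening differs by arm and the same share of worsened patients is withdrawn in both, the PANSS contrast is pulled towards zero, which hides a harm or a benefit of motivational interviewing (MI). If the discretionary share differs by arm, a false difference can appear, or a true one can be enlarged or reversed. Section 1 intends the effectiveness data to inform a large multicentre trial, so a biased estimate could be carried forward.

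**Working it through.** **The plan's own figure.** With f = 0.25, N = 128, two groups and two-sided alpha 0.05, the noncentrality is 128 × 0.25² = 8 on 1 and 126 degrees of freedom, and power is 0.801. N = 128 reproduces, and this point does not change it.

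**Tracing a worsened patient.**
1. Section 3.4 sends the reader to the exclusion criteria for what counts as progressed. In 3.1 the items that can arise during the study are substance abuse and stopping antipsychotics without the physician's agreement. Neither defines progression; no scale, threshold or assessor is given.
2. No section requires visit 7 after withdrawal. The only retention rule in 3.4 is for patients discharged early after at least three sessions.
3. Without a day-10 PANSS the ANCOVA has no outcome for that patient, and 4.2 excludes the record.

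**Illustrative size.** The documents give no rate of worsening or withdrawal, no PANSS change and no SD. Assumptions: worsened patients end 30 points above the others (range 20 to 40), residual SD 15, and replacement continues until 64 per arm complete. Let p be the worsening rate and w the share of worsened patients withdrawn. Among completers the worsened share is

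r = p(1 − w) / (1 − pw),

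and the PANSS difference is 30 × (r_MI − r_control). Negative favours MI.

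*No true difference:*

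| p, both arms | w, MI / control | r_MI − r_control | Difference (gap 20 to 40) |
|---|---|---|---|
| 10% | 0.6 / 0.4 | 0.0426 − 0.0625 | −0.6 (−0.4 to −0.8) |
| 5% | 0.8 / 0.2 | 0.0104 − 0.0404 | −0.9 (−0.6 to −1.2) |
| 10% | 0.8 / 0.2 | 0.0217 − 0.0816 | −1.8 (−1.2 to −2.4) |
| 20% | 0.8 / 0.2 | 0.0476 − 0.1667 | −3.6 (−2.4 to −4.8) |

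Swapping the shares flips the sign. Equal shares give zero.

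*True harm of MI of 3.0 points (p = 15% MI, 5% control; 30 × 0.10):*

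| w, MI / control | Difference seen |
|---|---|
| 0.5 / 0.5 | 30 × (0.0811 − 0.0256) = 1.7 |
| 1 / 1 | 0 |
| 1 / 0 | 30 × (0 − 0.05) = −1.5 |
| 0 / 1 | 30 × (0.15 − 0) = 4.5 |

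**Simulation** (10,000 trials per cell, ANCOVA, baseline correlation 0.5, same assumptions). With no true difference and 0.8 / 0.2 withdrawal, completer type I error is 9.4% at 10% worsening and 20.0% at 20%. When every day-10 PANSS is used it is 4.9% and 5.4%. The standard error is about 3 points, so most shifts are below one standard error. The largest, from 3.0 to −1.5, is 4.5 points, or about 1.6 standard errors using its SD of about 2.8.

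A separate model on a standardised scale, with any rise from baseline counted as worsening, gave −0.25 to +0.25 SD with no true effect. The sign depended on which arm lost more worsened patients.

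**The case against.** **Data of non-finishers may be used under 3.4.** True, so the text is not a pure completer rule. But the sentence sets no rule, sits awkwardly with 4.2, and cannot supply a score that was never taken.

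**The pointer may confine withdrawal to the listed criteria.** This reading is possible. If intended, 3.4 should say so. It is also why deleting the pointer would be wrong: that would leave an open-ended right.

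**The sizes are assumed, and 80% against 20% is extreme.** This stands. The milder split gives 0.6 points. Even with full retention, a 3-point harm is detected in only about 17% of trials. The gain is a less biased estimate, not a significant test.

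**Retention is itself selective.** This also stands. Section 3.4 says "Since they are inpatients, there is a very low risk of missed appointments", but that concerns inpatients in general, and 5.2 expects some worsened patients to refuse treatment. Take 10% worsening, half of the worsened withdrawn in each arm, no true effect, and attendance by 80% (MI) and 20% (control) of those withdrawn. Effective w becomes 0.5 × 0.2 = 0.1 and 0.5 × 0.8 = 0.4, and 30 × (0.0909 − 0.0625) = +0.85, where the completer analysis had no bias.

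**A stronger reading.** A reader might infer that the rule will favour MI, or that unblinded investigators will remove its failures. The documents do not support this. They do not show withdrawal differing by arm, and either direction is possible. Nor do they show that the primary endpoints are biased in this way: the completer rule covers STAR and BARS too, but the direct tie between the progression ground and the outcome is specific to PANSS.

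**Conclusion.** The concern holds as a gap in the rules. Undefined progression, discretionary withdrawal with replacement, and a completer analysis together allow patients to leave the Hypothesis 2 comparison because of the outcome being compared. The mechanism follows from the text; the size does not. Under the assumptions shown, the shift is 0.6 to 3.6 points at the 30-point gap with no true difference, and at most 4.5 when a 3-point harm is present and only worsened MI patients are withdrawn. If withdrawal is equally likely in both arms and there is no true effect, the bias is zero. Priority is modest, because PANSS is secondary and the study describes itself as an initial pilot. The change is worth making because it is cheap.

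**What to change.** **(a) Section 3.4.** Define progression by a stated criterion and assessor; do not merely delete the pointer. Make it a reason to stop sessions, not assessments. Add: *Patients withdrawn from the sessions who still consent have the scheduled day-10 assessment (visit 7).*

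**(b) Section 4.2, with the analysis-population paragraph in 4.1 aligned.** Replace the completer rule with one rule for all hypotheses: *Every randomised patient confirmed eligible at visit 2, judged on pre-intervention information only, who has the relevant post-measurement is analysed in the assigned arm, whether or not withdrawn or replaced. A patient missing one outcome is left out of that outcome's analysis only.* The visit 2 condition is needed because Table 2 randomises before the eligibility check. A rule for Hypothesis 2 alone would leave the primary endpoints without an analysis set.

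**(c) Reporting.** Give by arm the number randomised, found ineligible at visit 2, withdrawn for progression, and lacking a day-10 assessment, with reasons. Section 7.2 already records the reason for discontinuation. A table of serious adverse events is not needed here, since it would not correct the PANSS bias.

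**Cost.** Patients entered per arm, ignoring visit 2 exclusions, are 64 / (1 − pw). With p = 15% / 5% and w = 1 in both arms: 64/0.85 = 75.3 and 64/0.95 = 67.4, so 11.3 + 3.4, about 15, extra visits of up to 60 minutes. With p = 10% and w = 0.8 / 0.2: 64/0.92 = 69.6 and 64/0.98 = 65.3, so 5.6 + 1.3, about 7.

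**Limit.** Patients who refuse stay missing. If half of those withdrawn attend, equally by arm, w is halved: −1.8 becomes about −0.9, and the fully hidden 3.0 shows as 1.7. Unequal attendance can leave or create some bias, which is why (c) is needed.

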### *Expected relevance*

Therapeutic alliance during the acute phase of psychotic illness is one of the most pressing obstacles for successful long term recovery (e.g. Cavelti et al., 2016). In order for patients to accept much-needed medication and psychosocial therapy and not drop out prematurely, intrinsic motivation to adhere to therapy is crucial. Motivational Interviewing is a method, that has been developed and evaluated over the last three decades and that shows promising results, not only for patients with addiction but also for other patients who struggle with compliance and ambivalence towards treatment and change of behavior. For further information on the method see chapter 3.4. *Study intervention*.

At the same time, it is well known from clinical experience that patients are offered psychotherapy only late during the course of hospitalizations and not when it is most needed – during the acute phase of their illness. Accordingly, there is a clear gap in the literature as to which interventions are particularly useful in this challenging yet crucial phase of the illness.

We believe that the current project and the psychotherapeutic interventions tested here, can provide valuable data on acceptance, feasibility and effectiveness of such interventions and which can then be used to supplement a large multicentre trial across Switzerland.

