**3.3 Study procedures**

[figure not shown]
Time schedule

The study will last from October 2022 to September 2023.

- From October to December 2022, the study will be planned, and the ethics application will be written and submitted.
- From January, the concrete preparations will take place and
- from February 2023, the implementation will take place. The survey phase will last until August 2023.
- From August to October 2023, the study is to be evaluated, completed and the data analysed.

As can be seen in Table 2, the duration for each patient is between 13 and max. 16 days during their inpatient stay. The goal is to start with the study intervention as soon as possible after entering the psychiatric hospital.

Table 1: Study Flow Chart

**Table 2:** Overview study procedure

\* If questions / need for feedback occur after the last visit, an additional visit shall be provided

	Re-cruitment	Pre-Measurement	Intervention phase				Post-Measurement	
Visits	1 max. 30min.	2 max. 60min.	3 25- 40min .	4 25- 40min .	5 25- 40min .	6 25- 40min .	7 max. 60min.	Follow up max. 60min.
Time (days)	-3 +/-2d	0	2 +/-1d	4 +/-1d	6 +/-1d	8 +/-1d	10 +/-1d	60 +/-5d
Check with treating physician or psychologist	x							
Patient Information and Informed Consent	x							
Randomization	x							
Demographics and information about current treatment	x							
Examination of symptoms with PANSS and MATRICS		x					x	x
Control of In- and Exclusion Criteria		x						
Measurements of secondary outcome variables		x					x	
MI-Intervention (intervention group) or supportive conversations (controls)			x	x	x	x		
Possibility for patients to ask questions and give a feedback							x*	

Detailed description of the planned intervention

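### The discharge rule in section 3.4 leaves randomised patients who go home before the third session with no planned outcome visit

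*Combined protocol and SAP*

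**What the plan says.** Section 3.4 covers patients discharged before the study ends. They can come back for what is left of the schedule "if the majority of the study has already taken place (at least 3 psychotherapy sessions must have taken place during inpatient treatment". The condition applies to every later appointment, and outcome visits are not treated separately.

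Section 2.2 says of the primary endpoints, STAR and BARS: "These variables will be measured before and after the study intervention or control intervention". It gives the same timing for the secondary endpoints (PANSS, FPTM, GSE). Table 2 in section 3.3 places randomisation at visit 1 (day −3 ± 2), pre-measurement at day 0, session 3 at day 6 ± 1, session 4 at day 8 ± 1 and post-measurement (visit 7) at day 10 ± 1. It also has a column headed "Follow up max. 60min" at day 60 ± 5, where only the PANSS and MATRICS row is marked. Section 3.3 states that "the duration for each patient is between 13 and max. 16 days during their inpatient stay".

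Section 4.2 defines who is analysed: "All patients who completed the study will be taken into analysis". It also removes missing data. Section 3.4, by contrast, would use the data of non-finishers where feasible and worthwhile, and it replaces withdrawn participants.

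**The concern.** Whether a patient's outcome is measured depends on how long the patient stays on the ward, and that is settled after randomisation. Length of stay reflects the course of the episode and the patient's willingness to remain in care. Both are close to what the trial measures. Section 2.4 lists duration of hospital stay among the things earlier work says MI can influence. The section on expected relevance explains why motivation matters: "In order for patients to accept much-needed medication and psychosocial therapy and not drop out prematurely". So both treatment arm and prognosis could affect who passes the gate.

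This is more than a question of analysis set. An all-randomised analysis cannot use an outcome that was never collected, and replacement restores the number of patients but not the comparability of the arms. Two other parts of the plan also lose information. The regression on days of hospitalisation in section 4.1 would lack the shortest stays, and hypothesis 3, which concerns patients after they leave hospital, would lack the earliest leavers.

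**Working it through.** **1. Who is affected.** Count the admission day as hospital day 1.

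- Table 2 reproduces the stated duration: from visit 1 to visit 7 is 10 − (−3) = 13 days nominally and 11 − (−5) = 16 days at most.
- Recruitment is within the first three hospital days (section 3.1). Visit 2 follows visit 1 by 1 to 5 days, and session 3 follows visit 2 by 5 to 7 days.
- Earliest session 3: 1 + 1 + 5 = hospital day 7.
- Latest session 3: the windows alone give 3 + 5 + 7 = 15. Section 2.3 places pre-measurement within the first week, so the limit is 7 + 7 = hospital day 14.

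**2. What is lost.** Sections 2.2 and 3.3 together make visit 7 the only post-intervention measurement of STAR, BARS, FPTM and GSE. A patient without it has no value for the baseline-adjusted ANCOVA of section 4.1. The day-60 visit does not fill the gap. It is itself a later appointment under section 3.4, and neither primary endpoint is marked there.

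**3. Form of the bias.** Let q be the fraction of an arm discharged before session 3, and m the stayer-minus-leaver gap in SD after baseline adjustment, with higher scores better. The mean of stayers exceeds the mean of the whole arm by m × q. With the same gap in both arms,

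bias in (MI − control) = m × (q_MI − q_control).

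| | MI loses more | Control loses more |
|---|---|---|
| Leavers do worse (m > 0) | favours MI | against MI |
| Leavers do better (m < 0) | against MI | favours MI |

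The bias is zero when rates and leaver profiles are the same in both arms.

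**4. Illustrative size.** The documents give no discharge rate, so these inputs are assumptions. Take a 10-point difference in early discharge:

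- m = 0.3 SD: 0.3 × 0.10 = 0.03 SD.
- m = 0.8 SD: 0.8 × 0.10 = 0.08 SD.

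The gap must be the adjusted one. If leavers were 0.8 SD lower at both baseline and outcome, with a within-arm slope of 0.6, the adjusted gap would be 0.8 − 0.6 × 0.8 = 0.32 SD and the bias about 0.03 SD.

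The planned f = 0.25 equals d = 2 × 0.25 = 0.5 for two equal groups. Shifts of 0.03 to 0.08 SD are then 6% to 16% of the planned effect, or 10% to 27% of d = 0.3, the lower end of the range quoted in section 4.1. With no true effect, 64 analysed per arm and unit SD, the rejection probability of a two-sided 5% t test (noncentral t) is 5.9% at a shift of 0.05 SD and 8.7% at 0.10 SD.

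**5. Sample size.** The stated 64 per group reproduces: exact two-sided power at d = 0.5 is 80.1% with 64 per arm and 79.5% with 63. There is no allowance for loss. If early leavers were lost equally from both arms and not replaced:

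| Assumed loss | Analysed per arm | Power | Randomised N to keep 128 |
|---|---|---|---|
| 5% | 60 | 77.5% | 128/0.95 → 135 |
| 10% | 57 | 75.4% | 128/0.90 → 143 |
| 20% | 51 | 70.6% | 128/0.80 = 160 |
| 30% | 44 | 64.0% | 128/0.70 → 183 |

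**The case against.** The strongest reply is that section 3.4 grants permission and does not forbid anything. It never says that outcome visits are withheld, and it keeps non-finishers' data where useful. That is fair as far as it goes: the exclusion is by implication. But no other sentence schedules visit 7 for these patients, so staff following the text would not arrange it. A reader who infers an express ban goes further than the wording.

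A second reply is that differential discharge is unlikely to be large. Affected patients have had at most two sessions of 25 to 40 minutes, and both arms receive equal contact. This stands, and it limits how far the illustration can be pushed. A reader might infer that much of the planned effect could be lost: 5% versus 25% early discharge with a 0.8 SD gap gives 0.16 SD, and 30% versus 10% with a 1 SD gap gives 0.20 SD and a type I error of 20.2%. Nothing in the documents supports differences of that size, and those gaps ignore the baseline adjustment that section 4.1 specifies.

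Third, some patients who leave early would decline assessment anyway, so not all of the loss is due to the rule. STAR after zero to two sessions also reflects less contact than STAR after four. Both points stand. They are reasons to record sessions received, not reasons to leave the outcome uncollected.

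Finally, the day-60 visit might be read as proof that outpatient assessment is already a settled part of the design. That is weak. Section 3.3 gives 13 to 16 days per patient and section 6.1 limits the commitment to six sessions, and neither accommodates it. The better evidence of feasibility is that section 3.4 itself accepts outpatient attendance at visit 7 after three sessions.

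**Conclusion.** The point holds as a design weakness that is cheap to remove. As written, section 3.4 makes outcome measurement conditional on a post-randomisation event that may depend on arm and on outcome, and section 4.2 does not repair this. The range of 0.03 to 0.08 SD rests entirely on an assumed 10-point difference in early discharge and an assumed adjusted gap of 0.3 to 0.8 SD.

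A reader might conclude that the trial is biased against MI because MI keeps ambivalent patients on the ward. The documents do not support a direction. If MI instead speeds recovery and more MI patients leave early and well, the bias also runs against MI, while the other two combinations favour it. Section 2.4 itself says that data in schizophrenia remain insufficient.

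**What to change.** In section 3.4, separate outcome assessment from session attendance. State that visit 7 (day 10 ± 1) and the day-60 assessment already in Table 2 are sought for every randomised patient who has not withdrawn consent, regardless of sessions received or discharge date. Hold them as outpatient visits where needed. BARS is clinician-administered and PANSS is a structured interview, so both need an interview; the self-report forms can go by post or telephone. Record sessions received and discharge date, and report both by arm. Whether sessions themselves continue after discharge remains the trial team's decision.

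This works only if section 4.2 changes too. Replace the completer rule with analysis of all randomised patients as allocated, reconcile it with what section 3.4 says about non-finishers' data, and pre-specify a sensitivity analysis for outcomes that remain missing.

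The cost is an amendment to two sections and a few extra outpatient assessments by the existing raters. Some patients will still not return, and STAR in those with few sessions will need cautious interpretation.
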